#### Data Analysis:

Descriptive statistics will be used to summarize the children's demographic and polysomnographic characteristics. Comparisons between in laboratory sleep study and HST will be conducted using Mann Whitney U-Test for not-normal data, and Student's t-test for normally distributed variables. Factors that may have influenced the interpretability of the recordings will be investigated using logistic regression. Age, gender, AHI, and BMI z- scores will be analyzed as independent variables in the logistic regression equation. Odds ratios and their 95% confidence intervals (95% CI) will be calculated. A p-value <0.05 will be considered statistically significant. Any information that will be sent to the sponsor will be de-identified.

The criteria for an unfeasible HST or HST failure will be defined as:

1. Loss of the nasal flow channel, or thoracic or abdominal sensor
2. Recordings with less than 4h of artifact-free recording time
3. Less than 4h of SpO2 signal

All studies will be scored by a trained sleep technician, and interpreted by [name], in order to avoid variability. Both sleep scoring and sleep interpretations will be blinded from the findings of HST performed at home and in the sleep lab.

In the event that the HST is deemed not valid or inadequate when compared to the in laboratory PSG, the subject will remain in the study and will use this data to evaluate validity and feasibility of HST. Information

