**6. SPECIFIC AIMS**

1. To determine validity, feasibility, and accuracy of HST as a diagnostic tool for assessing children over the age of 12 for diagnosing OSA in children with symptoms compatible with OSA
2. To assess patient satisfaction with HST compared to in laboratory PSG in the diagnostic work up for pediatric OSA.

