Applicability of HST in children is rather limited as many children are intolerant to specific devices including the nasal cannula resulting in data collection that is lower quality or unacceptable altogether. Certainly, this limited tolerance is anticipated more often in younger children. Despite this preliminary studies have been encouraging. Brockman et al demonstrated a 93% success rate of HST conducted in children with an average age of 2.8 years of age and found no difference in success rates between in laboratory PSG and HST. A recent systematic review corroborated the above conclusions and revealed a sensitivity of 76%, a specificity of 77%, and an area under the curve of 0.88 which attested to the fact that unattended HST perform well for predicting pediatric OSA. However, further studies enabling head-to-head comparisons and validation of specific clinical algorithms are needed. The inability to determine total sleep time absence of EEG testing and subsequent inability to score respiratory events that culminate in arousal as opposed to desaturation and finally inability to identify sleep architecture can culminate the utility of HST particularly in young children. While these issues may be more problematic in young children, HST may be more useful in adolescents with OSA as OSA during adolescence parallels what is observed in adults

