### Experimental procedure:

Of the twenty children recruited, ten will undergo home sleep testing (HST) no greater than one week prior to their in-laboratory PSG, while the other ten children will undergo HST no greater than one week following their in laboratory PSG. Participants who are randomized to receive the HST prior to their in-laboratory PSG will have the Resmed ApneaLink Air mailed to their home address. This will avoid the additional need for a study visit. All twenty children will also undergo their HST concurrent to their in-laboratory PSG. The rational for splitting children in these two groups is to equally distribute the effects of the first night evenly, in which

the sleep architecture including reduced total REM sleep time can vary in some children during their first ever sleep study. As the HST will be compared to the in-lab PSG, we would like to evenly distribute this effect by having two groups of ten children.

Upon obtaining consent by the PI, [name], or the research coordinator, [name], the subject will be provided with a verbal explanation and instructions on how to use the device. These instructions (both Spanish and English version) will also be included with the device they will take home at the time of their sleep lab appointment. Information about how to apply the ApneaLink Air device at home will be demonstrated by sleep technologists who are members of the research team. A hotline number will be provided to the patients and parents in order to answer questions or problem solve.

For home sleep testing (HST), the participants will use the Resmed ApneaLink Air™ device (Resmed, San Diego, USA). The ApneaLink Air is a device used to assess for sleep-disordered breathing. ApneaLink Air records five channels of information: respiratory effort, pulse and pulse oxygen saturation, nasal flow, body position and snoring. It includes a chest belt, nasal cannula, oximeter and recording device. This device is approved by the FDA for use in diagnosing OSA in adults. This device is not yet approved for use in the proposed subject population (12-17 years old) and the data obtained from this study may be used for the application of an FDA approval for children over 12. No clinical interventions will be implemented based on the results of the home sleep test.

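### The only planned HST-versus-PSG comparison is a Mann-Whitney or t-test, which cannot show agreement or diagnostic accuracy in the same child; Mann-Whitney also ignores the pairing

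*Combined protocol and SAP*

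**What the plan says.** Section 6 states the first aim: "To determine validity, feasibility, and accuracy of HST as a diagnostic tool for assessing children over the age of 12". Section 9 (Experimental procedure) sets a within-child design: "All twenty children will also undergo their HST concurrent to their in-laboratory PSG". Each child also wears the device for one night at home, within a week before or after the laboratory night.

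Section 9 (Data Analysis) gives the comparison: "Comparisons between in laboratory sleep study and HST will be conducted using Mann Whitney U-Test for not-normal data", "and Student's t-test for normally distributed variables". It adds "A p-value <0.05 will be considered statistically significant". The t-test is not said to be paired or unpaired. The same section plans a logistic regression for the interpretability of recordings and lists criteria for a failed HST. Both concern feasibility; neither compares HST with PSG.

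Section 7 describes earlier home testing in accuracy terms: a systematic review "revealed a sensitivity of 76%, a specificity of 77%, and an area under the curve of 0.88". The visible text plans none of these measures for this study and states no AHI cut-off for obstructive sleep apnea (OSA). Data Analysis foresees that an HST may be judged invalid against PSG but gives no criterion for that judgement.

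**The concern.** There are two separate problems.

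1. **The test answers a different question.** Validity and accuracy concern the individual child: does HST give nearly the same AHI, and the same OSA diagnosis, as PSG? A test of location asks only whether the two sets of values are centred in the same place. Errors of opposite sign cancel. A significant result does not show that HST is clinically inadequate, and a non-significant one does not show that it agrees with PSG.

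2. **Mann-Whitney does not fit the design.** It treats the two sets of readings as coming from different children. When readings from the same child are positively correlated, the test overstates the sampling error of the difference and loses power to detect a systematic shift. Section 7 gives reasons to expect such a shift: "The inability to determine total sleep time absence of EEG testing and subsequent inability to score respiratory events that culminate in arousal".

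The stakes go beyond a local report, because section 9 says "the data obtained from this study may be used for the application of an FDA approval for children over 12".

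**Working it through.** The plan gives no power, SD, expected bias or precision target, so it has no figure to reproduce.

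**Inputs from the document.** 20 children, each measured by both methods (section 9); significance at p<0.05 (Data Analysis), taken as two-sided.

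**Assumptions.** Bivariate normal readings with SD 1 for each method, within-child correlation r, and HST shifted from PSG by a stated number of SDs. The document gives neither r nor the shift, so a range is shown. Each setting used 20,000 simulated studies (4,000 for Wilcoxon).

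**Step 1: can a non-significant result show agreement?** Set r = 0, so that HST carries no information about PSG in the same child. The 95% limits of agreement are then ±1.96 × √(2(1 − 0)) = ±2.77 SD. Share of studies with p ≥ 0.05:

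| Shift (SD) | Unpaired t | Paired t | Mann-Whitney | Wilcoxon signed-rank |
|---|---|---|---|---|
| 0 | 94.9% | 95.0% | 95.0% | 95.2% |
| 0.5 | 65.4% | 67.0% | 67.3% | 68.8% |
| 1 | 13.0% | 14.9% | 14.8% | 15.9% |

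The first row is 1 − α, so a larger sample does not change it, and pairing the test does not help. An extreme case makes the same point: take 20 PSG values and reassign them at random among the children as the HST values. Mann-Whitney, the unpaired t-test and the paired t-test then all return p = 1.0.

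**Step 2: what does ignoring the pairing cost?** Take a shift of 0.5 SD. The standard error of the mean difference is √(2(1 − r)/20); an unpaired test uses about √(2/20) = 0.316 whatever r is. At r = 0.9 the correct value is √(0.2/20) = 0.10. The shift is therefore 0.5/0.10 = 5.0 standard errors in a paired test but registers as only 0.5/0.316 = 1.6 in an unpaired one. Simulated share missing the 0.5 SD shift:

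| r | Mann-Whitney | Wilcoxon signed-rank | Unpaired t | Paired t |
|---|---|---|---|---|
| 0.9 | 81.1% | 0.3% | 83.2% | 0.3% |
| 0.8 | 78.3% | 9.2% | 78.6% | 8.2% |
| 0.7 | 75.5% | 24.3% | 75.0% | 21.4% |

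The unpaired t column applies only if the plan's t-test is run unpaired. With 16 usable recordings and r = 0.9, Mann-Whitney misses 88.5% and Wilcoxon 1.9%.

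**Step 3: other shifts and skewed data** (4,000 runs per setting, r from 0.9 to 0.7). Mann-Whitney misses about 12% to 23% at 0.8 SD and 1% to 5% at 1 SD. At 0.2 SD and r = 0.7, even Wilcoxon misses about 82%. On lognormal data with a 0.5 SD log-scale shift, Mann-Whitney is unchanged at 76% to 81%, and Wilcoxon on the raw scale misses 2% to 32%.

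**Step 4: what 20 children can support instead.**

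- *Limits of agreement.* The 95% CI half-width for each limit, in SDs of the paired differences, is t(0.975, n − 1) × √(1/n + 1.96²/(2(n − 1))). For n = 20 this is 2.093 × √(1/20 + 3.8416/38) = 2.093 × 0.389 = 0.81. For n = 16 it is 2.131 × √(1/16 + 3.8416/30) = 2.131 × 0.437 = 0.93.
- *Sensitivity.* Exact (Clopper-Pearson) 95% intervals near the 76% cited in section 7 are 44% to 97% for 8/10, 45% to 92% for 11/15, and 28% to 99% for 4/5. The number of OSA-positive children is an assumption.

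**The case against.** The strongest points on the other side are these.

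- *The text may be incomplete.* Data Analysis breaks off mid-sentence in the available text, just after it mentions HST judged invalid against PSG. A criterion could have followed. Statements about what is absent are therefore limited to the visible text. However, the statistical paragraph comes earlier and is complete, and the tests it names are unsuitable whatever followed.
- *Student's t-test includes the paired version.* This stands. The t-test is unclear rather than wrong, and the pairing error is established only for Mann-Whitney. Pairing would not cure the first problem.
- *The simulated cases are chosen.* Zero correlation is a logical limit, not a forecast: in the laboratory one cannula feeds both systems, so the concurrent readings should correlate. The loss from ignoring the pairing is largest for moderate shifts, shrinks at 0.8 to 1 SD, and is somewhat smaller on skewed data. The direction stays the same.
- *The plan never says that p>0.05 means valid.* True, but the visible text gives no other basis for judging validity or accuracy.
- *It is a small study, no treatment follows from the HST result, and regulatory use is only a possibility.* This limits direct harm to participants. A small sample justifies wide intervals, not an analysis that does not address the aim.

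**Conclusion.** The concern holds. Followed as written, the plan gives no sound answer on the validity or accuracy of HST, which are two of the three parts of Aim 1. That a difference test cannot establish agreement is a matter of logic and needs no assumed values. The cost of ignoring the pairing does depend on assumptions: for a 0.5 SD bias and correlations of 0.7 to 0.9, Mann-Whitney misses about three-quarters to four-fifths of the time, against 24% down to 0.3% for its paired counterpart. Replacing Mann-Whitney with Wilcoxon would cure only the second problem. The point must be fixed before scoring begins, because a cut-off chosen after the results are seen can bias sensitivity and specificity. The feasibility part of Aim 1 is not affected.

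**What to change.** Rewrite the comparison paragraph in section 9 (Data Analysis) as follows.

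1. **Agreement in AHI.** Report the Bland-Altman mean difference and 95% limits of agreement, each with a 95% CI, on a log scale if the data are skewed.
2. **Diagnostic accuracy.** Report sensitivity and specificity of HST against PSG with exact 95% CIs, at a PSG AHI cut-off chosen and justified by the investigators and fixed before scoring. State the rule that makes an HST positive.
3. **Two settings.** Report both analyses separately for the HST concurrent with PSG and for the home HST. The first isolates the device; the second adds the change of night and setting.
4. **Any test of bias.** Use a paired t-test or Wilcoxon signed-rank test, and state that p>0.05 will not be read as agreement.
5. **Failed recordings.** Report accuracy in all children tested, counting recordings that meet the plan's failure criteria as non-diagnostic, and again in interpretable recordings only.

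The cost is a rewritten paragraph and the work of justifying a cut-off, with no new children or recordings. The intervals will be visibly wide, and wider if recordings fail. The change makes the analysis fit the aim; it does not make 20 children enough for a conclusive statement on accuracy.

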This device is a non-significant risk device as it poses minimal risk or clinical harm to the pediatric population. The following criteria for a device to be deemed non-significant risk are met:

1. The device is NOT intended as an implant that presents a potential for serious risk to health, safety, or welfare of a subject
2. The device is NOT purported or represented to be for a use in supporting or sustaining human life that presents a potential for serious risk to the health, safety, or welfare of a subject
3. The device is NOT for a use of substantial importance in diagnosing, curing, mitigating, or treating disease, or otherwise preventing impairment of human health that presents a potential for serious risk to the health, safety, or welfare of a subject
4. The device does NOT otherwise present a potential for serious risk to the health, safety, welfare of a subject.

Furthermore, adolescents with suspected OSA (the study population) tend to parallel the OSA presentation of adults. Thus, no additional risk, other than those for adults, will incur to the patient if the device is used by the study population.

As stated, all subjects will have ApneaLink Air performed twice, once at home, and once during the sleep study. All of the components of the ApneaLink Air device will be placed in addition to the equipment used in the sleep lab. With exception to the nasal cannula, this should not interfere or result in additional discomfort to the in-lab sleep study. With regards to the nasal cannula, a 'splitter' will be used in which one nasal cannula will provide information on flow to both the ApneaLink Air device as well as the in-laboratory lab equipment (Nihon Koden, Irvine CA)

For ApneaLink Air testing performed at home, these subjects will receive a shipping box and return label to return the device following completion.

All children undergoing sleep study testing will have routine clinical surveys be performed. Some of this information will be gathered for research purposes to assess the pre-test probability of OSA. Following the home sleep test and in lab sleep test, all children will be interviewed by the research coordinator and asked questions concerning the child's experiences and comparing the two environments for their sleep test via a

telephone follow-up.

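### The PSG-HST comparison is within child, but the plan names Mann-Whitney U, a test for independent groups, leaves the t-test form unstated, and names no paired method

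*Combined protocol and SAP*

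**What the plan says.** The Data Analysis part of section 9 of the combined protocol and SAP gives one rule for comparing the two methods: "Comparisons between in laboratory sleep study and HST will be conducted using Mann Whitney U-Test for not-normal data, and Student's t-test for normally distributed variables". A p-value below 0.05 counts as significant. Sidedness is not stated, and there is no rule for interpreting a non-significant result. The only other inferential method is a logistic regression on what affects the interpretability of recordings.

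The Experimental procedure part of section 9 sets the data structure. For the laboratory night: "All twenty children will also undergo their HST concurrent to their in-laboratory PSG". Overall, "all subjects will have ApneaLink Air performed twice, once at home, and once during the sleep study". On the laboratory night the two systems share a flow signal: "one nasal cannula will provide information on flow to both the ApneaLink Air device as well as the in-laboratory lab equipment". Ten children do the home test up to a week before PSG and ten up to a week after. The stated purpose is order balance: "The rational for splitting children in these two groups is to equally distribute the effects of the first night evenly".

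The comparison serves Aim 1 in section 6: "To determine validity, feasibility, and accuracy of HST as a diagnostic tool".

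**The concern.** Each child contributes a PSG value and two device values, so PSG and HST results come in matched sets. The test named for non-normal data treats them as if they came from two unrelated groups of children. The test named for normal data has a paired and a two-sample form, and the plan does not choose. Its place beside Mann-Whitney hints at the two-sample form, but that is an inference.

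If PSG and HST are positively correlated within child, an independent-groups test leaves the between-child variation in the error term. It becomes too conservative and can miss a moderate systematic under- or over-reading by the device. In a validation study that is the unsafe direction if a non-significant difference is then taken as support for validity. The plan neither says it will be read that way nor rules it out. The Experimental procedure part adds that the data may be used to seek FDA approval in this age group.

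The Data Analysis part also does not say whether PSG is compared with the concurrent recording, the home recording or both.

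**Working it through.** **Inputs from the documents.** 20 children (section 9, Target Population); one PSG and two device recordings per child (Experimental procedure); significance at p < 0.05 (Data Analysis), taken here as two-sided. The documents give no power, SD, effect size or correlation, so there is no planned figure to reproduce.

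**Assumptions.** 20 complete pairs, bivariate normal, equal SDs, within-child correlation rho varied over a range, and a fixed device bias in SD units.

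**Step 1: error term.** The true standard error of the mean difference is sqrt(2(1 − rho)/n) SD. The two-sample form uses sqrt(2/n) SD, which is too large by 1/sqrt(1 − rho):
- rho 0.5: 1/sqrt(0.5) = 1.41
- rho 0.8: 1/sqrt(0.2) = 2.24

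**Step 2: half-width of the 95% CI for the mean difference.**
- Unpaired: t(0.975, 38) × sqrt(2/20) = 0.64 SD at any rho.
- Paired: t(0.975, 19) × sqrt(2(1 − rho)/20) = 0.55, 0.47, 0.36, 0.30 and 0.21 SD at rho 0.3, 0.5, 0.7, 0.8 and 0.9.

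**Step 3: difference detectable with 80% power** (normal approximation).
- Unpaired: sqrt(2/20) × (1.960 + 0.842) = 0.89 SD.
- Paired, multiplying by sqrt(1 − rho): 0.63, 0.49, 0.40 and 0.28 SD at rho 0.5, 0.7, 0.8 and 0.9.

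**Step 4: power for a 0.5 SD bias**, by simulation (100,000 samples per setting for the t-tests, 20,000 for the rank tests).

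| Assumed rho | Mann-Whitney | Signed-rank | Unpaired t | Paired t |
|---|---|---|---|---|
| 0 | 32% | 31% | 34% | 32% |
| 0.3 | 29% | 41% | 31% | 43% |
| 0.5 | 27% | 54% | 29% | 56% |
| 0.7 | 24% | 76% | 25% | 78% |
| 0.8 | 22% | 91% | 22% | 92% |
| 0.9 | 20% | 99.5% | 17% | 99.7% |

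The noncentral t distribution gives the same paired-t power. For skewed data (lognormal, log-SD 1, shift of 0.5 log-SD) the pattern holds: Mann-Whitney against signed-rank is 27% against 48% at rho 0.5, and 22% against 84% at rho 0.8.

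**Step 5: other bias sizes.** At 0.3 SD and rho 0.8, power is 3% (Mann-Whitney) and 2% (unpaired t), against 50% (signed-rank) and 53% (paired t). At 0.9 SD the unpaired t still reaches 83% to 97% for rho 0.3 to 0.9, against 90% to 100% paired. The loss therefore concerns small and moderate bias.

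**Step 6: actual size of the nominal 5% test.** For Mann-Whitney it is 5.0% at rho 0, 2.0% at 0.3, 0.9% at 0.5 and 0.1% at 0.7. The paired tests stay between 4.4% and 5.2%.

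High rho is more plausible for the concurrent recording (same night, shared cannula). It may be lower for a home night up to a week away.

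**The case against.** - **Only half of the rule is definitely wrong.** The wording "Student's t-test for normally distributed variables" covers the paired form. This stands: the unpaired-t figures describe one possible reading, and only the Mann-Whitney figures describe a named test.
- **The error is conservative.** It raises no false alarm of device bias, and no sentence says that p ≥ 0.05 means agreement. This also stands, so the harm to validity is conditional. The loss of power is not conditional on how the result is read.
- **The gain depends on rho and on complete pairs.** HST failures are foreseeable. With an assumed 16 pairs and a 0.5 SD bias, paired-t power falls to 35%, 47% and 68% at rho 0.3, 0.5 and 0.7. At low rho the sample size is a limit whichever test is used. This qualifies the size of the effect, not the mismatch.
- **The design rationale points to the home recording.** The split is justified by first-night effects on the comparison with PSG. That is a fair hint, but whether the concurrent recording is also tested remains unstated.
- **A paired test does not establish agreement or accuracy.** True, and an agreement analysis matters more for Aim 1. That does not justify keeping an invalid comparison in the plan. The pairing stays in the data, but choosing the test after seeing the data is what a plan should prevent.

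Two further defences fail. The two groups of ten are independent of each other, but the quoted rule compares PSG with HST, not one order group with the other. The Data Analysis text breaks off mid-sentence, but it does so after the handling of inadequate HSTs, and the sentence naming the tests is complete.

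**Conclusion.** The concern holds, and the rule is wrong as written. Mann-Whitney U does not fit a comparison in which every child supplies both measurements, and the visible text names no paired alternative. The t-test form is an ambiguity rather than a demonstrated error. The mismatch follows from the design and needs no assumption. Its cost rests on the assumed rho, equal SDs and 20 complete pairs: none at rho 0, about half the power for a 0.5 SD bias at rho 0.5, and about three quarters of it at rho 0.8. Bias near 0.9 SD would usually be found either way. The claim that the error favours the device applies only if non-significance is taken as agreement.

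**What to change.** In the Data Analysis part of section 9:

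1. Replace the named tests with a paired t-test on within-child differences, or the Wilcoxon signed-rank test if the differences (not the raw values) are not normal.
2. Report the mean or median difference with a 95% CI.
3. Do this separately for concurrent HST against PSG and for home HST against PSG.
4. State that a non-significant difference will not be taken as evidence of agreement. The paired test does not replace an agreement analysis for Aim 1.

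Optional additions, on which the point does not depend: account for test order in the home comparison, for example by regressing the within-child difference on order; and, if failure rates of the two recordings are to be compared, use the exact McNemar test.

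The cost is a change of test names and a few sentences, made before the analysis. No extra data, staff or patients are needed.

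### The one reader-blinding rule masks reads from HST findings but does not, as worded, mask HST scoring and interpretation from the PSG

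*Combined protocol and SAP*

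**What the plan says.** Section 9, Data Analysis, first says who reads: "All studies will be scored by a trained sleep technician", with a single named interpreter, so as to limit variability. The blinding rule follows at once: "Both sleep scoring and sleep interpretations will be blinded from the findings of HST performed at home and in the sleep lab".

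The Experimental procedure part of section 9 says where HST takes place: "all subjects will have ApneaLink Air performed twice, once at home, and once during the sleep study". Ten children have the home test in the week before the PSG and ten in the week after. All twenty also wear the device on the PSG night, when "one nasal cannula will provide information on flow to both the ApneaLink Air device as well as the in-laboratory lab equipment".

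Three criteria define a failed HST: loss of the flow channel or an effort sensor; "Recordings with less than 4h of artifact-free recording time"; and under 4 hours of oximetry signal. If an HST is judged inadequate against the PSG, "the subject will remain in the study and will use this data to evaluate validity and feasibility of HST".

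The available text gives no reading order and does not say whether device output is scored by hand or by software. It ends partway through a sentence in Data Analysis, and some pages are not available, so statements about what is absent apply to the available text only.

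**The concern.** HST is the index test and PSG the reference. In an accuracy study both directions of masking matter. The direction that most directly protects the claim about the new test is reading that test without the reference result. A scorer who knows that the PSG showed many events, or few, can resolve borderline events and doubtful signal in the same direction. Agreement then looks better than it would in practice, where no PSG is to hand.

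The rule as worded secures the other direction only. Aim 1 (section 6) is the validity and accuracy of HST, and section 9 adds that "the data obtained from this study may be used for the application of an FDA approval for children over 12". Anyone assessing such an application would ask whether HST was read without the PSG, and the plan gives no clear answer.

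**Working it through.** No figure in the plan bears on this point, so the check is a reading of the text followed by a count.

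**1. What does the rule hide?** It hides findings of HST in two places, home and sleep laboratory. The Experimental procedure confirms that HST is done in both. The phrase therefore has a ready literal meaning, the two HST recordings, and need not refer to the PSG.

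**2. Whose reading does it cover?** There are three possible readings:

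| Reading of the rule | PSG read masked from HST? | HST read masked from PSG? |
|---|---|---|
| A. It covers PSG scoring and interpretation only | Yes | Not addressed |
| B. It covers all studies, taken literally | Yes | No; an HST read is masked only from HST findings, which makes sense only as the child's other HST |
| C. It is loose wording for home test versus laboratory test | Yes | Yes |

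Only C masks HST reads from the PSG, and C requires departing from the literal wording.

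**3. Is the gap closed elsewhere?** No. The coding and de-identification text in sections 9, 11, 12, 15 and 16 concerns confidentiality. No separate HST readers and no reading sequence are described.

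**4. How many recordings are involved?**
- HST recordings: 20 children x 2 = 40.
- Made on the PSG night: 20. Made at home after the PSG: 10. Together 20 + 10 = 30 of 40 are made during or after the PSG.
- The other 10 precede the PSG but could still be read after it, since no order is set.
- The number read with the PSG known could therefore be anywhere from 0 to 40.

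**5. Where does judgement enter?** It enters event scoring and interpretation, and at least two of the three failure criteria. Channel loss has no stated duration or threshold, and artifact-free time depends on what is called artifact. The oximetry criterion is closer to a count.

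**The case against.** The strongest reply is that this is loose drafting, not a decision to leave HST reads unmasked. The rule directly follows a sentence about all studies, and elsewhere section 9 contrasts the two settings in similar terms: "Following the home sleep test and in lab sleep test". Mutual masking is a natural intention. That stands, and it is why the point concerns what the rule secures as worded. It does not remove the point, because staff who followed the sentence exactly could still read HST with the PSG known.

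A second reply is that automatic scoring would reduce the exposure. That is correct for event scoring, but the plan does not state the method, and interpretation and failure calls would remain. Equally, if the sentence about all studies was not meant to include HST, shared readers are not established; but then no rule on HST reading is given at all.

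Four stronger readings are tempting, and the documents do not support them:
- *HST is read unblinded.* Nowhere stated; the plan merely fails to rule it out.
- *HSTs that disagree with the PSG are dropped.* The plan says the opposite: such children stay in and their data are used.
- *The shared cannula defeats masking on the PSG night.* A split flow signal does not show a reader the PSG scoring. It shows only that masking could stay incomplete for those 20 recordings.
- *The bias can be bounded from the pooled accuracy in section 7 (sensitivity 76%, specificity 77%).* At prevalence p, discordance would be p x 0.24 + (1 - p) x 0.23, or 23% to 24%, which is 4.6 to 4.8 of 20 pairs. Treating that as possible inflation assumes that pooled figures not specific to this device apply here, that every pair is evaluable, that every discordant call moves to the PSG, and that a yes/no comparison is made. The plan specifies no such comparison; it names Mann-Whitney and t-tests. The figure should carry no weight.

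**Conclusion.** The point holds as a gap in the stated masking. The rule protects the PSG from the HST, and as worded does not protect the HST from the PSG. The likely direction of any bias is towards higher apparent agreement. Its size cannot be derived from the documents and may be nil if mutual masking is in fact practised.

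The conclusion rests on the plain reading of one sentence and on the available text containing no other blinding rule. Confidence is medium for that reason. This is a cheap improvement: it should be made before reading begins, and it does not by itself discredit the design.

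**What to change.** Replace the blinding sentence in section 9, Data Analysis, with:

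> PSG scoring and interpretation will be blinded to both HSTs; HST scoring and interpretation, including all HST failure calls (channel loss and artifact-free time), will be blinded to the PSG and to the child's other HST.

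To make this work in practice:
- Give each HST file a code separate from the participant code, with the key held by someone who does not score or interpret.
- Read HST files apart from the PSGs, with the same readers, which keeps the plan's aim of limiting variability. Batching is optional.
- Lock each HST AHI and failure call before linking it to the PSG, and judge HST adequacy against the PSG only after that lock.
- State whether device output is scored by hand or automatically.

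The cost is one amended sentence, some file handling for 40 recordings, and slightly later HST reads. The delay should be tolerable, since section 9 says that home results will not drive any clinical intervention. One limit remains: masking could stay incomplete for the 20 same-night recordings, because one cannula feeds both systems. The report should say so.
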